4.2 Heterogeneity analysis

Heterogeneity by baseline mental health status. For our primary outcome and for selected secondary outcomes such as take-up of the app, we will analyze heterogeneity by baseline mental health status, as measured by the PHQ-ADS. This heterogeneity is policy-relevant, because policy-makers may especially value students at high risk of anxiety and depression receiving therapy. It also conceptually relates to our treatments, in that screening might be expected to cause more positive selection on symptoms of depression and anxiety while rewards have ambiguous selection effects.

The standard cutoffs in scores in the PHQ-ADS scale in the literature are 10-19 for mild symptoms, 20-29 for moderate symptoms, and 30 or higher for severe symptoms. We will combine the moderate and severe categories in our analysis, as only a small share of students are expected to show severe symptoms.

We will estimate the following regression:

$$Y_i = \alpha + \beta T_i + \gamma T_i \times \text{Mild}_i + \theta T_i \times \text{Moderate or Severe}_i + \lambda X'_i + \epsilon_i$$

for each of the pooled treatment indicators and outcome variables. The vector of controls X_i includes the indicator variables Mild_i and $\text{Moderate or Severe}_i$.

We will also run a model which interacts the treatments with a continuous measure of the PHQ-ADS score:

$$Y_i = \alpha + \beta T_i + \gamma T_i \times \text{PHQ-ADS}_i + \lambda X'_i + \epsilon_i$$

where X_i is the vector of controls now including the continuous measure of PHQ-ADS score.

Heterogeneity by other characteristics. As exploratory analyses, we will examine heterogeneity by other baseline characteristics, such as participants' financial status, their perception of their mental health status, and their major sources of stress.

Heterogeneity by other characteristics.

5 Funding and Human Subjects Review

The study has been funded by The Weiss Fund for Research in Development Economics, Solomon Buchsbaum Research Fund, [name]'s and [name]'s discretionary research funds from Harvard University, and [name]'s discretionary research funds from MIT in the past and is currently being funded by [name]'s discretionary research funds from University of California, Berkeley. The IRB at MIT is serving as the primary institution of record (protocol 2206000666), and has entered into a reliance agreement with Harvard University, University of California, Berkeley, and University of Michigan. The IRB at IFMR has also approved the study.

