2.2 Treatments

Treatments are randomized at the individual level, stratified by categories of PHQ-ADS scores. Treatment status will be revealed via the survey administered through students' mobile phones. Participants will be randomized to four conditions:

1. **Control:** The control group will (a) watch a video introducing them to the mental health services available in the college, including introductory videos of the counselors, (b) have access to therapy at no cost for the duration of the study via their college counselors and additionally at SCARF, a mental health center in Chennai, and (c) be given links to book a therapy session or download a mental health app.
2. **Screening:** In addition to the interventions in the control group, students in the screening group will receive feedback on their PHQ-ADS score and recommendations based on that. In particular, they will be informed whether their responses to the PHQ-ADS questions fit in the standard risk categories of no, mild, moderate, or severe distress and corresponding recommendations for whether to make an appointment with a counselor/therapist.
3. **Rewards:** In addition to the interventions in the control group, students in the rewards group will be provided with a cash payment of Rs. 500 (USD 5.70 at market exchange rates) for attending a (first) therapy session.
4. **Screening and rewards:** Students in this group will receive both interventions, i.e., both the screening information and the reward described above.

For ethical reasons, participants with PHQ-ADS scores of 30 or above (indicating severe risk of depression and anxiety) in the non-screening treatment arms will also be informed of their scores at the end of the survey. For outcome variables measured within the survey, we will treat these participants as though they are part of the group to which they are randomly assigned. One outcome variable (completing the process to make an appointment for therapy) is measured after the conclusion of the participant survey. For this outcome variable, we will separately run regressions both including and excluding these individuals.

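### For appointments and attendance, merging severe with moderate scores in 4.2 blurs the screening effect in the high-risk group, because severe students are told their score in every arm and the planned exclusion is one-sided

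*Combined protocol and SAP*

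**What the plan says.** Section 2.2 provides that participants scoring 30 or above "in the non-screening treatment arms will also be informed of their scores at the end of the survey". It sees the timing problem this creates: "One outcome variable (completing the process to make an appointment for therapy) is measured after the conclusion of the participant survey". Its remedy follows: "For this outcome variable, we will separately run regressions both including and excluding these individuals". The individuals meant are the severe students in the non-screening arms. Nothing says that severe students in the screening arms are dropped too.

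Section 4.2 gives the cutoffs as "10-19 for mild symptoms, 20-29 for moderate symptoms, and 30 or higher for severe symptoms", and then says: "We will combine the moderate and severe categories in our analysis". The reason it gives is that few students should score as severe. The categorical interaction model is to be run for each pooled treatment and outcome. The baseline controls in section 4.1 use the same three levels, with moderate and severe together. Section 4.2 mentions neither the disclosure nor the include/exclude rule.

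Making an appointment is one of the two primary outcomes (section 3.1). Attendance of therapy sessions (section 3.2) comes from counselling-office records and so is also recorded after the survey, but the rule in section 2.2 covers a single outcome and attendance is not it.

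**The concern.** By the time appointments are counted, every severe student in every arm has been told their score. Moderate students in the non-screening arms have not, so they give a clean randomised contrast of screening against no feedback. Putting both in one cell mixes a clean contrast with a reduced one.

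Excluding the disclosed students as section 2.2 words it does not restore a clean contrast. It leaves moderate plus severe students on the screened side and moderate students alone on the unscreened side.

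Section 4.2 justifies this analysis by the policy value of reaching high-risk students and by the expectation that screening selects on symptoms. The high-risk cell is therefore the one that most needs a clear interpretation, and for a primary outcome the two planned versions could give noticeably different answers there.

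**Working it through.** The plan gives no severe share, booking rate or effect size, so there is no figure of its own to reproduce. All numerical inputs below are assumptions.

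**Notation, for the Moderate or Severe cell**
- s: severe share of the cell.
- d: effect of feedback on booking, taken as equal in moderate and severe students.
- c: fraction of d that the end-of-survey disclosure produces.
- pm, ps: booking rates without feedback in moderate and severe students.

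The quantity examined is the screening effect in the cell, beta + theta. In the section 4.2 model, theta alone is the difference from the no-risk group. If the no-risk effect beta is unaffected, theta shifts by the same number of points.

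**1. Everyone included.** Moderate students contribute (1 - s) x d. Severe students contribute s x d x (1 - c). The sum is d(1 - s x c). With d = 10 points:

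| s | c = 1 | c = 0.5 |
|---|---|---|
| 5% | 9.5 | 9.75 |
| 25% | 7.5 | 8.75 |
| 35% | 6.5 | 8.25 |

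**2. Excluded as worded (non-screening arms only).** The screened mean is (1 - s)(pm + d) + s(ps + d) = pm + d + s(ps - pm). The unscreened mean is pm. The difference is d + s(ps - pm), so the shift is s(ps - pm) before other controls.
- With d = 0, s = 25%, pm = 8% and ps = 16%: 0.75 x 8% + 0.25 x 16% = 10%, against 8%. The cell shows +2.0 points where there is no effect.
- With the same 8-point gap, s = 5% gives 0.05 x 8 = 0.4 points and s = 35% gives 0.35 x 8 = 2.8 points.
- The merged-category control does not remove the shift, because it does not separate severe from moderate.

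**3. Excluded from all four arms.** The screened mean is pm + d and the unscreened mean is pm. The difference is d, for moderate students, whatever s is.

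**4. Simulation check.** One least-squares fit of the section 4.2 model without the other controls used n = 400,000, s = 20% (6% of all students severe and 24% moderate: 6/30), c = 1, d = 10 points, pm = 10% and ps = 20%.

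| Version | Formula | Simulated |
|---|---|---|
| Merged, everyone included | 8.0 | 7.8 |
| Merged, one-sided exclusion | 12.0 | 11.9 |
| Severe dropped from all arms | 10.0 | 9.6 |
| Separate severe term: moderate effect | 10.0 | 9.6 |
| Separate severe term: severe contrast | 0 | 0.2 |

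The standard error of the moderate estimate is about sqrt((0.10 x 0.90 + 0.20 x 0.80)/48,000) = 0.23 points, so 9.6 agrees with 10 within simulation error.

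**5. Continuous-score model.** With everyone included, the contrast is attenuated above 29, which distorts the slope. One-sided exclusion acts on the score, which this model controls for, so it causes no bias if booking is linear in the score. Any bias then depends on curvature.

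**6. Rewards.** Severe students are informed both with and without rewards, so the pooled rewards contrast is not differentially affected.

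**The case against.** The plan's authors have seen the problem. Section 2.2 names the disclosure, notes that appointments come after it, and commits to two sets of regressions. The wording is general enough to cover section 4.2. This stands, so the plan cannot be said to overlook the issue. What remains is that section 4.2 does not say the rule applies there, and that the rule, read literally, is one-sided.

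The root cause is the disclosure, not the merging. The pooled and saturated models of section 4.1 are affected as well, and separating the categories cleans only the moderate term. This also stands. Merging matters because it passes the loss on to students who did not have it.

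If severe students book more and feedback raises booking, the two planned versions lie on either side of the moderate effect. That is true under those signs, but the gap can be wide: at s = 25%, c = 1, d = 10 and an 8-point booking gap, they would read 7.5 and 12.0.

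Section 4.2 expects few severe students. That refers to all students. The share within the merged cell must be larger as long as some students fall in the lower categories, and it is not stated. At s = 5% and c = 1 the attenuation is only half a point.

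Severe students may keep some contrast. The screening arms get a risk category and recommendations. The other arms are told only the score, as far as the text says, and only at the end of the survey. Hence c = 1 is a worst case. Controls such as mood, perceived mental health, past care and baseline interest in therapy may also absorb part of the one-sided shift.

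**Conclusion.** The point holds in a limited form. For appointments and attendance, the merged cell does not isolate screening against no feedback in high-risk students.
- **Including everyone:** attenuated to d(1 - s x c). For an assumed 10-point effect and s of 5% to 35%, that is 9.5 to 6.5 points at c = 1 and 9.75 to 8.25 at c = 0.5.
- **Excluding as worded:** shifted by about s(ps - pm) before other controls, upward if severe students book more.

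The sizes rest wholly on assumed values of s, c and the booking rates. The direction of the second error rests on ps exceeding pm.

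A reader might infer more than the documents support:
- That neither version is valid. The including version is a randomised comparison and is unbiased for assignment to screening as delivered, with severe students informed in all arms.
- That severe students carry no contrast at all. The text leaves room for some.
- That theta itself shrinks in proportion to s. The figures describe beta + theta.
- That the slope model fails in the same way under exclusion. It does not if booking is linear in the score.

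This should be corrected before analysis, but it does not undermine the trial's main comparisons.

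**What to change.** State in sections 2.2 and 4.2, for appointments and for attendance:
- The excluding regressions drop scores of 30 or above from all four arms, and the section 4.2 group is then labelled moderate. This conditions only on a baseline score, so randomisation is preserved.
- The including regressions give 30 or above its own indicator and its own treatment-by-severe term, interpreted as a contrast between two informed groups. This term belongs only in the including version. Under one-sided exclusion every remaining severe student is screened, and the term could not be separated from the severe indicator.
- The continuous-score interaction is also reported on scores 0 to 29, mainly to remove attenuation at the top of the scale.

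Keep the merged category for outcomes measured within the survey, which precede the disclosure.

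The cost is a change of wording and one more indicator with its interaction. Precision falls slightly, and the clean high-risk estimate covers moderate scores only. No analysis choice can recover screening against no feedback in severe students, because no severe student remains uninformed when these outcomes are recorded.
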